5.8. Drug Dispensation and Accountability

The investigators and/or pharmacists must maintain records of the IP's delivery to the study site, the IP inventory at the site, the use by each subject, and the return to the sponsor or alternative disposition of unused IP. These records will include dates of administration, batch/serial numbers, expiration time/dates and the subject (randomization) number assigned to the study subject. At the time of return to the sponsor or alternative disposition, investigators must verify that all unused or partially used IP have been returned by the investigational sites and no remaining IP is in the investigators' possession.

The investigator or his/her delegate should complete the Study Treatment Record in the CRF.

5.9. Treatment exposure and compliance

All subjects will be administered LMIS 50mg via subcutaneous injection at the study site. The administration of the IP to the subject is under the supervision of the Investigator and controlled by the clinical site personnel delegated IP dispensing, preparation and administration roles by PI.

5.10. Treatment for Investigational Product Overdose

The single-dose LMIS 50 mg will be carefully administered to each subject in up to two doses 6 months apart by investigators or professional clinical site personnel officially delegated that responsibility by the investigator. If any accidental overdose injection is given, the subject should be closely monitored for safety until terminated from the study.

6. Study Procedures

This is a multi-center, open-label, single-arm safety extension study. After completing 12 months of treatment with LMIS 50 mg under Protocol FP01C-13-001 (with last dose under Protocol FP01C-13-001 approximately 6 months prior to Day 0 or Protocol FP01C-13-001-EX) and providing a written informed consent, subjects will be screened against baseline inclusion/exclusion criteria necessary for study eligibility. Eligible subjects will receive LMIS 50 mg from the prefilled syringes (without dilution or other mixing) in up to two single subcutaneous injections given 6 months apart.

After a single administration on Day 0, subjects will be evaluated, blood and urine samples collected, and other procedures performed as shown in the [Table 1](#). The sign "X" indicates when the procedure should take place.

Subjects who withdraw from the study prematurely for any reason during the study period will undergo the assessments listed for the final (End of Study/Early Termination) visit. If a subject refuses to return for these assessments or is unable to do so, every effort should be made to contact him or a knowledgeable informant by telephone to determine his condition. Documentation of attempts to contact the subject should be recorded in the medical chart and CRF.

Table 1 Schedule of Assessments

	Scrn ¹ (Subjects from FP01C-13-001 who completed study more than 28 days ago)	Scrn ² (Subjects who completed the study within the last 28 days)	Treatment				ET ⁴ /EOS
Visit	1	1	2	3	4	5	6
Day (from completion of 12 months of treatment with LMIS 50 mg under FP01C-13-001)	-28-0	-28-0	0	84	168 ³	252	336
Informed consent	X	X					
Inclusion/Exclusion criteria	X	X					
Demographics	X	X					
Vital signs and height and weight ⁵ (resting 3 minutes)	X	X	X	X	X	X	X
ECOG PS	X	X					
Physical Exam	X			X	X	X	X
12-Lead ECG (Supine 5 minutes)	X				X		X
Laboratory							
Hematology ⁶	X			X	X	X	X
Biochemistry ⁷ (Fasting)	X			X	X	X	X
Urinalysis ⁸	X			X	X	X	X
HgbA1c (Fasting)	X						X
PSA	X			X	X	X	X
Testosterone	X				X ⁹		
Study treatment			X		X		
Concomitant treatments			X	X	X	X	X
Adverse events	X	X	X	X	X	X	X

Scrn: Screening; EOS: End of study; ET: Early termination; BP: Blood pressure; HR: Heart rate; RR: Respiratory rate; BT: Body temperature

¹. If the patient completed 12 months of treatment with LMIS 50 mg more than 28 days prior to entering the Extension study, the testosterone level should be repeated and the repeat test should indicate that the patient maintains a castrate-level of testosterone. In addition, the ECOG, PE, ECG, laboratory and PSA tests should be repeated.

- ² If the patient has completed 12 months of treatment with LMIS 50 mg under Protocol FP01C-13-001 within the last 28 days, they will be allowed to enter the Extension study without repeating the testosterone measurements, ECG, PE, laboratory and the PSA tests.
- ³ If the Day 168 (2nd injection, Visit 4) is delayed, have the subject return for subsequent visits according to the date when the first injection was received. DO NOT ADJUST THE TIMELINE DUE TO THE LATE INJECTION
- ⁴ For early termination subjects (ET), procedures indicated should be performed. In addition, phone contacts should be performed at 3 and 6 months after the last injection of study drug to collect drug-related AEs, concomitant medication or non-drug therapy received for AEs treatment, disease progression status, and subject survival status.
- ⁵ Vital signs include BP, HR, RR, and BT. Subject weight will be measured at Screening and EOS.
- ⁶ Hematology tests include CBC, such as Hb, Hct, RBC count, WBC count with differential and platelet count.
- ⁷ Biochemistry tests include ALT, AST, ALP, total bilirubin, BUN, Serum Cr, electrolytes (K, Na, Mg, Ca and P), blood glucose, and lipid profile (LDL, HDL, triglycerides)
- ⁸ Urinalysis tests include pH, specific gravity, leukocyte, erythrocyte, protein.
- ⁹ Testosterone Level test (Optional item depending on investigators' judgment)

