4.1. Inclusion Criteria*

- (1) Complete 12 months of treatment with LMIS 50 mg under Protocol FP01C-13-001. If a subject wishes to enter the Extension study after more than 28 days following his end of study visit for Protocol FP01C-13-001, his serum testosterone level should be repeated at the screening visit to confirm that his castrate-level testosterone has been maintained.
- (2) Laboratory values
 - o Absolute neutrophil count \geq 1,500 cells/ μ L
 - o Platelets \geq 100,000 cells/ μ L
 - o Hemoglobin \geq 10 gm/dL
 - o Total bilirubin \leq 1.5 \times upper limit of normal (ULN)
 - o AST (SGOT) \leq 2.5 \times ULN
 - o ALT (SGPT) \leq 2.5 \times ULN
 - o Serum creatinine \leq 1.5 mg/dL
 - o Lipid profile within acceptable range according to investigator's opinion
 - o Serum glucose within acceptable range according to investigator's opinion
 - o HgbA1c within acceptable range according to investigator's opinion
 - o Clinical chemistries (K, Na, Mg, Ca and P) within acceptable range according to investigator's judgment
 - o Urinalysis within normal range according to the investigator's judgment
- (3) Agree to use male contraceptive methods during study trial
- (4) In the Investigator's opinion, the ability to understand the nature of the study and any hazards of participation, and to communicate satisfactorily with the Investigator and to participate in, and to comply with, the requirements of the entire protocol
- (5) All aspects of the protocol explained and written informed consent obtained

*If the patient completed 12 months of treatment with LMIS 50 mg more than 28 days prior to entering the Extension study, the ECOG, PE, ECG, laboratory and PSA tests should be repeated.

If the patient has completed 12 months of treatment with LMIS 50 mg under Protocol FP01C-13-001 within the last 28 days, they will be allowed to enter the Extension study without repeating the testosterone measurements, ECG, PE, laboratory and the PSA tests

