6.1. Screening Visit (Day -28 ~0 from End of Study Visit for FP01C-13-001)

At the Screening Visit, informed consent must be obtained from the subject prior to performing any procedures related to the study and after the subject has received sufficient information about the study.

Subjects who have been screened should be listed in the Screening Log. Moreover, all screening procedures conducted must be documented in the CRF. If the subject fails screening or decides not to continue in the study, the primary reason should be documented in the CRF. No data will be entered into the database for screened subjects who do not meet criteria for entering the study or decide not to continue in the study. No CRF sections other than the screening section will be completed for these subjects.

Inclusion/exclusion criteria should be checked during this visit. The following study procedures will be conducted for screening assessments.

- (1) Record date that informed consent was signed. The following should be documented in the subject's medical chart: that they are participating in this study, document that informed consent has been obtained, and that a copy of the consent has been given to the subject.
- (2) The Screening number for this study will be the Study Number used under Protocol FP01C-13-001
- (3) Update the Medical History from what was collected under Protocol FP01C-13-001
- (4) Update the medical/tumor history and medication from what was collected under Protocol FP01C-13-001
- (5) Conduct a complete physical examination, including measurement of body weight (and body height as measured in Protocol FP01C-13-001). Measure and record the vital signs (after a 3 minute seated rest) including the measurement of blood pressure, heart rate, respiratory rate, and body temperature
- (6) 12-Lead ECG (supine for at least 5 minutes)
- (7) Record the ECOG PS
- (8) Collect fasting blood sample for analysis of:
 - o Hematology: CBC, including Hb, Hct, RBC count, WBC count, WBC differential and platelet count
 - o Biochemistry: ALT, AST, ALP, total bilirubin, BUN, Serum Cr, electrolytes (K, Na, Mg, Ca and P), blood glucose, lipid profile (LDL, HDL, triglycerides)
 - o PSA level
 - o HgbA1c
- (9) Collect urine sample for urinalysis test
 - o pH, specific gravity, leukocyte, erythrocyte, protein

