(10) Record any pre-treatment AE(s) NOTE: Open AEs from Protocol FP01C-13-001 will be recorded in this study file and noted in the database and other study documentation as, "AE under Protocol FP01C-13-001." These AEs should not be counted twice in the overall safety database.

*If the patient completed 12 months of treatment with LMIS 50 mg more than 28 days prior to entering the Extension study, the testosterone level should be repeated and the repeat test should indicate that the patient maintains a castrate-level of testosterone. In addition, the ECOG, PE, ECG, laboratory and PSA tests should be repeated.

If the patient has completed 12 months of treatment with LMIS 50 mg under Protocol FP01C-13-001 within the last 28 days, they will be allowed to enter the Extension study without repeating the testosterone measurements, ECG, PE, laboratory and the PSA tests.

6.2. Day 0 (approximately 6 months from last dose of LMIS 50 mg under Protocol FP01C-13-001)

Perform the following at 0 hr:

- (1) Record subject enrollment number prior to dosing (same enrollment number as was used in FP01C-13-001 will be used in this study)
- (2) Record vital signs prior to dosing
- (3) Record concomitant medication(s) prior to dosing
- (4) Record AE(s) prior to dosing and post dosing
- (5) Administer LMIS 50 mg.

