9. EXTENT OF EXPOSURE AND DRUG COMPLIANCE

The treatment duration (days) is defined as (last administered date – first administered date + 1); and the study duration (days) is defined as (last visit date – first administered date + 1).

The treatment duration (days) and study duration (days) will be summarized by the number of observations (n), mean, median, standard deviation (SD), standard error, minimum and maximum. The summary results will be presented as Table 14.3.2. Also, the proportion of subjects received first and second administration has been provided as Table 14.3.2.

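### The schedule's Day row counts from parent-study completion while the dosing text counts from the first extension injection; for men who enter later, the two give different injection and visit dates.

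*Protocol*

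**What the plan says.** The schedule of assessments appears three times: synopsis XI, Table 1 in protocol Section 6, and SAP 3.4. In each, the day count is labelled "Day (from completion of 12 months of treatment with LMIS 50 mg under FP01C-13-001" and runs 0, 84, 168, 252, 336, with study treatment on Days 0 and 168. The dosing line in synopsis III places the two injections at Months 12 and 18 from the start of the parent study, in the same sentence that separates them by 6 months.

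Other passages use other origins:

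- Section 6 makes Day 0 the injection day ("After a single administration on Day 0") and has LMIS given "in up to two single subcutaneous injections given 6 months apart". Sections 5.1 and 5.10 give the same interval.
- Footnote 3 of the schedule, for a late second injection, tells sites to "have the subject return for subsequent visits according to the date when the first injection was received".
- Section 6.2 is headed "Day 0 (approximately 6 months from last dose of LMIS 50 mg under Protocol FP01C-13-001", which ties Day 0 to the last parent dose.
- Section 6.1 is headed "Screening Visit (Day -28 ~0 from End of Study Visit for FP01C-13-001", which ties screening to the parent end-of-study visit.
- Sections 6.3 to 6.6 give Days 84, 168, 252 and 336, each ±7 days, without naming an origin.

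Inclusion criterion 1 (Section 4.1) provides for a man who "wishes to enter the Extension study after more than 28 days following his end of study visit", and the schedule has a separate screening column for such men.

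**The concern.** A schedule can have only one Day 0. Here it is the day of parent completion by the row label and the day of the first extension injection by Section 6. For a man who moves straight from one study to the other, this makes no difference. For a man who enters later, the row label and the 6-month requirement cannot both hold, and neither can the two halves of the synopsis dosing sentence.

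Two things are at stake. One is the timing of a depot injection that the protocol describes as releasing drug over 6 months. The other is the meaning of the results: SAP 10.3 and 10.4 and the table shells summarise and test change from baseline at Day 168 and Day 336, and the SAP gives no visit-window rule. If sites anchor differently, those columns pool different times since dosing.

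**Working it through.** **Inputs.** The second injection is on Day 168 ± 7 (Section 6.4) and the last visit on Day 336 ± 7 (Section 6.6). The first injection is on Day 0 (Section 6). Let g be the days from parent completion to the first extension injection. The documents give no distribution for g. They say only that some men enter more than 28 days after the parent end-of-study visit, so the values below are assumptions. I take completion of parent treatment and the parent end-of-study visit as the same date.

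**Formulas.**

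- Day row read literally: first to second injection = 168 - g, window (161 - g) to (175 - g). First injection to last visit = 336 - g.
- Counted from the first injection: 168, window 161 to 175, and 336, whatever g is.

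**The plan's own figures.** At g = 0 both readings give 168 and 336, so the printed schedule is reproduced for a man injected on the day of parent completion.

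| g (days) | Second injection after first, Day row (window) | Counted from first injection (window) | Last visit after first injection, Day row | Injection windows |
|---|---|---|---|---|
| 0 | 168 (161–175) | 168 (161–175) | 336 | identical |
| 7 | 161 (154–168) | 168 (161–175) | 329 | overlap |
| 14 | 154 (147–161) | 168 (161–175) | 322 | touch at day 161 |
| 15 | 153 (146–160) | 168 (161–175) | 321 | disjoint |
| 28 | 140 (133–147) | 168 (161–175) | 308 | disjoint |
| 29 | 139 (132–146) | 168 (161–175) | 307 | disjoint |
| 56 | 112 (105–119) | 168 (161–175) | 280 | disjoint |
| 84 | 84 (77–91) | 168 (161–175) | 252 | disjoint |

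**Where the readings separate.** The nominal days differ by g, so they differ by more than the 7-day tolerance once g > 7. The windows are disjoint when 175 - g < 161, that is, when g > 14. Every late entrant (g of at least 29) is past that point. So is a man in the other screening column who is injected 15 to 28 days after completion.

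**Effect on one summary.** SAP 9 defines treatment duration as last minus first administration date plus 1. At g = 29 that is 139 + 1 = 140 days on one reading and 168 + 1 = 169 on the other.

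**Screening.** Section 6.1 and the first screening column place screening at Day -28 to 0, measured from the parent end-of-study visit or parent completion. A man screened more than 28 days after that visit is at Day +29 or later. The window has already closed for the men the column was written for.

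**The case against.** The strongest reply is that the troublesome reading cannot be carried out from the start. For a late entrant the row label's Day 0 has already passed, so nobody can inject him on it. A site has to treat the injection day as Day 0 to use the table at all, and Section 6 supports that. A second injection at 139 days would also run against the interval in Sections 5.1, 5.10 and 6. This has force. It means a reader should not infer that the schedule instructs sites to overlap depots, or that sites did so; the documents do not show how any site acted. It does not remove the conflict, because the Month 18 entry in the synopsis independently supports the parent-study clock for the second injection.

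Four other inferences go further than the text allows:

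- **Footnote 3 sets the injection interval.** It does not. It times only the visits that follow a delayed second injection.
- **Section 6.2 counts from the first extension injection.** Its heading names a third origin, the last parent dose. Only its procedure list puts the injection on Day 0.
- **The SAP definitions are part of the conflict.** SAP 9 states that "the study duration (days) is defined as (last visit date – first administered date + 1", and Onset Day likewise starts at first administration. These are analysis variables and do not contradict a visit table. With the dose dates in Listing 16.2.5.2, they would make variation in the interval visible.
- **The entry gap is unrestricted.** No maximum in days is stated, but Day 0 is to be about 6 months after the last parent dose, late entrants need a repeat testosterone at castrate level, and dosing is limited by drug expiry (May 31, 2016, possibly Nov 30, 2016). Large values of g are therefore illustrations only.

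**Conclusion.** The inconsistency is real and lies in the text. The Day row (three tables) and the synopsis Month 12 and Month 18 entries use a parent-study clock. Sections 5.1, 5.10 and 6 require a 6-month separation starting from an injection on Day 0. For anyone with g above 0 they diverge by g days, and for every late entrant by at least 29 days. The screening window for late entrants is impossible as written.

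The size rests on the assumed g and on a literal reading of the row label. The number of men affected is not given, and sites may have resolved the ambiguity in the sensible way. This is a conflict to be reconciled in the operative schedule. It is not evidence of mistimed doses, and it touches no sample size or hypothesis test. It still deserves correction because it governs when an injection is given and what Day 168 and Day 336 mean in the safety tables.

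**What to change.** State one day-count origin, chosen by the sponsor, and use it in the synopsis III dosing line, synopsis XI, Table 1, Sections 6.1 to 6.6 and SAP 3.4, so that every passage yields the same interval between injections. State a screening window on that origin that a man entering more than 28 days after the parent end-of-study visit can meet. No dosing interval is proposed here; the passages only have to agree.

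Leave the 28-day retest rule alone. It concerns time since parent completion, and moving it would change an eligibility rule. The SAP duration and Onset Day definitions can also stay as they are.

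The cost is a wording change in the protocol and a matching edit to the SAP schedule, with no new visits, tests or patients.

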6.1. Screening Visit (Day -28 ~0 from End of Study Visit for FP01C-13-001)

At the Screening Visit, informed consent must be obtained from the subject prior to performing any procedures related to the study and after the subject has received sufficient information about the study.

Subjects who have been screened should be listed in the Screening Log. Moreover, all screening procedures conducted must be documented in the CRF. If the subject fails screening or decides not to continue in the study, the primary reason should be documented in the CRF. No data will be entered into the database for screened subjects who do not meet criteria for entering the study or decide not to continue in the study. No CRF sections other than the screening section will be completed for these subjects.

Inclusion/exclusion criteria should be checked during this visit. The following study procedures will be conducted for screening assessments.

- (1) Record date that informed consent was signed. The following should be documented in the subject's medical chart: that they are participating in this study, document that informed consent has been obtained, and that a copy of the consent has been given to the subject.
- (2) The Screening number for this study will be the Study Number used under Protocol FP01C-13-001
- (3) Update the Medical History from what was collected under Protocol FP01C-13-001
- (4) Update the medical/tumor history and medication from what was collected under Protocol FP01C-13-001
- (5) Conduct a complete physical examination, including measurement of body weight (and body height as measured in Protocol FP01C-13-001). Measure and record the vital signs (after a 3 minute seated rest) including the measurement of blood pressure, heart rate, respiratory rate, and body temperature
- (6) 12-Lead ECG (supine for at least 5 minutes)
- (7) Record the ECOG PS
- (8) Collect fasting blood sample for analysis of:
 - o Hematology: CBC, including Hb, Hct, RBC count, WBC count, WBC differential and platelet count
 - o Biochemistry: ALT, AST, ALP, total bilirubin, BUN, Serum Cr, electrolytes (K, Na, Mg, Ca and P), blood glucose, lipid profile (LDL, HDL, triglycerides)
 - o PSA level
 - o HgbA1c
- (9) Collect urine sample for urinalysis test
 - o pH, specific gravity, leukocyte, erythrocyte, protein

(10) Record any pre-treatment AE(s) NOTE: Open AEs from Protocol FP01C-13-001 will be recorded in this study file and noted in the database and other study documentation as, "AE under Protocol FP01C-13-001." These AEs should not be counted twice in the overall safety database.

*If the patient completed 12 months of treatment with LMIS 50 mg more than 28 days prior to entering the Extension study, the testosterone level should be repeated and the repeat test should indicate that the patient maintains a castrate-level of testosterone. In addition, the ECOG, PE, ECG, laboratory and PSA tests should be repeated.

If the patient has completed 12 months of treatment with LMIS 50 mg under Protocol FP01C-13-001 within the last 28 days, they will be allowed to enter the Extension study without repeating the testosterone measurements, ECG, PE, laboratory and the PSA tests.

6.2. Day 0 (approximately 6 months from last dose of LMIS 50 mg under Protocol FP01C-13-001)

Perform the following at 0 hr:

- (1) Record subject enrollment number prior to dosing (same enrollment number as was used in FP01C-13-001 will be used in this study)
- (2) Record vital signs prior to dosing
- (3) Record concomitant medication(s) prior to dosing
- (4) Record AE(s) prior to dosing and post dosing
- (5) Administer LMIS 50 mg.

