9.1. Adverse events (AEs)

An adverse event (AE) is defined as any untoward medical occurrence in a subject or clinical investigation subject administered a pharmaceutical product which does not necessarily have a causal relationship with the treatment. An AE can therefore be any unfavorable and unintended sign, symptom, or disease temporally associated with the use of a medicinal product, whether or not considered related to the medicinal product. However, abnormal laboratory values or changes are not automatically reported as adverse events if they are not clinically significant. They will only be recorded as adverse events if a therapeutic action is needed or the investigator judges them to be clinically significant.

The occurrence of adverse events should be sought by non-directive questioning of the subject at each visit and/or telephone follow-up during the study. Adverse events also may be detected when they are volunteered by the subject during or between visits or through physical examination, vital sign measurement, laboratory test or other assessments. All adverse events must be recorded on the Adverse Events CRF with the following information:

1. AE term and description
2. Duration (onset and resolution dates or if continuing at final exam)
3. Severity grade (mild, moderate, severe, life-threatening, death)
4. Whether the AE constitutes a serious adverse event (SAE)
5. Relationship to the study drug (definite/possible/unrelated)
6. Action taken and treatment required
7. Outcome (recovered/resolved, recovered/resolved with sequelae, recovering/resolving, not recovered/not resolved, fetal)

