10. SAFETY ANALYSIS

10.1 Adverse Events

All AEs (whether treatment related or not) that occur before, during, or after dosing of the study medication will be recorded. The verbatim adverse event (AE) terms will be coded using the MedDRA dictionary, version18.1 or highest, and classified by System Organ

Statistical Analysis Plan

Class and Preferred Term.

Adverse events will be categorized as:

- Previous treatment-emergent adverse event (TEAE): The TEAEs are captured from previous FP01C-13-001 study.
- Newly treatment-emergent adverse event (TEAE): AEs occurring during or after the treatment period until the subject is off study, or before the first administration of study drug and worsen in severity for this FP01C-13-001-EX study.

Total treatment-emergent adverse event (TEAE): The combination of previous TEAEs and Newly TEAEs.

Unless otherwise specified, all adverse event summaries will include the previous TEAEs, Newly TEAEs and Total TEAEs. The listing of all TEAEs will be provided in Listing 16.2.7.1.

All AEs will be summarized by CTCAE version 4 grade and MedDRA preferred terms. The severity will be graded as follows:

- Grade 1 Mild; asymptomatic or mild symptoms; clinical or diagnostic observations only; intervention not indicated
- Grade 2 Moderate; minimal, local or noninvasive intervention indicated; limiting age-appropriate instrumental activities of daily living* (ADL)
- Grade 3 Severe or medically significant but not immediately life-threatening; hospitalization or prolongation of hospitalization indicated; disabling; limiting self-care ADL**
- Grade 4 Life-threatening consequences; urgent intervention indicated
- Grade 5 Death related to AE

Activities of Daily Living (ADL):

*Instrumental ADL refer to preparing meals, shopping for groceries or clothes, using the telephone, managing money, etc.

**Self-care ADL refer to bathing, dressing and undressing, feeding self, using the toilet, taking medications, and not bedridden.

The reasonable possibility of causation will be determined based on the investigator's clinical judgment as follows:

- **Definite:** A clinical event, including laboratory test abnormality, occurring in a plausible time relationship to drug administration, and which cannot be explained by concurrent disease or other drugs or chemicals.

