System Organ Class 2	Preferred Term 1	E	nn	(xx.x%)	E	nn	(xx.x%)	E	nn	(xx.x%)	
System Organ Class 2	Preferred Term 2	E	nn	(xx.x%)	E	nn	(xx.x%)	E	nn	(xx.x%)	
Moderate AE											
System Organ Class 1	Preferred Term 1	E	nn	(xx.x%)	E	nn	(xx.x%)	E	nn	(xx.x%)	
System Organ Class 1	Preferred Term 2	E	nn	(xx.x%)	E	nn	(xx.x%)	E	nn	(xx.x%)	
System Organ Class 2	Preferred Term 1	E	nn	(xx.x%)	E	nn	(xx.x%)	E	nn	(xx.x%)	
System Organ Class 2	Preferred Term 2	E	nn	(xx.x%)	E	nn	(xx.x%)	E	nn	(xx.x%)	
Severe AE											
System Organ Class 1	Preferred Term 1	E	nn	(xx.x%)	E	nn	(xx.x%)	E	nn	(xx.x%)	
System Organ Class 1	Preferred Term 2	E	nn	(xx.x%)	E	nn	(xx.x%)	E	nn	(xx.x%)	
System Organ Class 2	Preferred Term 1	E	nn	(xx.x%)	E	nn	(xx.x%)	E	nn	(xx.x%)	
System Organ Class 2	Preferred Term 2	E	nn	(xx.x%)	E	nn	(xx.x%)	E	nn	(xx.x%)	
Life-threatening AE											
System Organ Class 1	Preferred Term 1	E	nn	(xx.x%)	E	nn	(xx.x%)	E	nn	(xx.x%)	
System Organ Class 1	Preferred Term 2	E	nn	(xx.x%)	E	nn	(xx.x%)	E	nn	(xx.x%)	
System Organ Class 2	Preferred Term 1	E	nn	(xx.x%)	E	nn	(xx.x%)	E	nn	(xx.x%)	
System Organ Class 2	Preferred Term 2	E	nn	(xx.x%)	E	nn	(xx.x%)	E	nn	(xx.x%)	
Death AE											
System Organ Class 1	Preferred Term 1	E	nn	(xx.x%)	E	nn	(xx.x%)	E	nn	(xx.x%)	
System Organ Class 1	Preferred Term 2	E	nn	(xx.x%)	E	nn	(xx.x%)	E	nn	(xx.x%)	
System Organ Class 2	Preferred Term 1	E	nn	(xx.x%)	E	nn	(xx.x%)	E	nn	(xx.x%)	
System Organ Class 2	Preferred Term 2	E	nn	(xx.x%)	E	nn	(xx.x%)	E	nn	(xx.x%)	

E is the number of events, n is the number of subjects, and the AE percentage: 100%*The number of subjects with event (n) / Total number of subjects in Safety population (N)
[Program: \\Foresee\\FP01C-13-001\\SAP\\Table\\S_AE.sas]

Table 14.3.1.6: Summary of Incidence of SAEs (Safety Population)

System Organ Class / Preferred Term	Previous TEAEs (N=XX)			Newly TEAEs (N=XX)			Total TEAEs (N=XX)		
	E	n	(%)	E	n	(%)	E	n	(%)
System Organ Class 1									
Preferred Term 1	E	nn	(xx.x%)	E	nn	(xx.x%)	E	nn	(xx.x%)
Preferred Term 2	E	nn	(xx.x%)	E	nn	(xx.x%)	E	nn	(xx.x%)
System Organ Class 2									
Preferred Term 1	E	nn	(xx.x%)	E	nn	(xx.x%)	E	nn	(xx.x%)
Preferred Term 2	E	nn	(xx.x%)	E	nn	(xx.x%)	E	nn	(xx.x%)

E is the number of events, n is the number of subjects, and the AE percentage: 100%*The number of subjects with event (n) / Total number of subjects in Safety population (N)
 [Program: \\Foresee\\FP01C-13-001\\SAP\\Table\\S_AE.sas]

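### A parent-study adverse event that first becomes serious in the extension without a change of grade is tabulated as a Previous and Total SAE, but not as a Newly SAE

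*Protocol*

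**What the plan says.** Protocol section 6.1, item (10), states: "Open AEs from Protocol FP01C-13-001 will be recorded in this study file and noted in the database". Such events are labelled as belonging to the parent protocol, and the item continues: "These AEs should not be counted twice in the overall safety database".

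SAP section 10.1 sets up three categories.

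- Previous: "The TEAEs are captured from previous FP01C-13-001 study".
- Newly: events occurring in or after the extension treatment period until the man leaves the study, "or before the first administration of study drug and worsen in severity for this FP01C-13-001-EX study".
- Total: "The combination of previous TEAEs and Newly TEAEs".

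The same section says that, unless otherwise specified, "all adverse event summaries will include the previous TEAEs, Newly TEAEs and Total TEAEs". The shells for Table 14.3.1.1, which has an SAE row, and for SAE Table 14.3.1.6 both carry these three columns.

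Severity and seriousness are separate items on the adverse event form (Protocol section 9.1, items 3 and 4). Severity is one CTCAE grade per event, the maximum reached over its duration (section 9.1.1). Seriousness is a single classification per event, made against the criteria in section 9.2. No field is specified for the date on which an event became serious.

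**The concern.** The extension exists to describe safety during a second year of exposure, and the Newly column separates that year from the first. For an event already open at entry, the only way into that column is a rise in grade. An event can become serious without one, and the rule then leaves it in the column for the parent study.

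At stake is the SAE incidence reported for the extension year. The numbers are likely to be small, so the placement of one man is visible in the result. The listings do not clearly correct the tables. Listing 16.2.7.3 gives onset and resolution dates and an onset day counted from first administration, but not the date on which the event became serious. An event that began in the parent study therefore shows a parent-study onset whenever the serious episode occurred.

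**Working it through.** The plan gives no figure to reproduce: no sample size was calculated and no SAE rate is assumed. The check applies the definitions to each possible case and then scales the effect of one man.

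**Step 1. Can an event become serious with no rise in grade?** Compare Protocol Table 9-1 with section 9.2.

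- The Grade 3 description already includes an indication for hospitalization. An event graded 3 in year 1 without admission can lead to admission in year 2 and remain Grade 3.
- An important medical event is serious by medical judgment, and that criterion is not tied to a grade.
- Because the recorded grade is the maximum over the whole event, one that peaked at Grade 3 in year 1, eased while still open, and returned to Grade 3 with an admission shows no rise.
- A fatal outcome is Grade 5 and a life-threatening one is Grade 4. If the event was at a lower grade before, these count as worsening and qualify as Newly.

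**Step 2. Apply SAP section 10.1.** Each event is kept as one record, and its serious item is up to date in the extension file.

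| Onset | Grade worsened in extension | Serious | Definitions met (SAE tables) |
|---|---|---|---|
| Parent study | No | Yes, first in year 2 | Previous (hence Total) |
| Parent study | Yes | Yes | Previous and Newly (hence Total) |
| Extension | Either | Yes | Newly (hence Total) |

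The first row is the fault. The second shows a related gap: an event that worsens meets both definitions. If Total were formed by adding the columns, its event count would be 1 + 1 = 2 for one event, against Protocol 6.1 (10). The SAP does not say how Total avoids this.

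**Step 3. Size of one misplaced man.** The tables use incidence = 100 × n/N, with N the Safety population. One man changes it by 100 × 1/N percentage points. SAP section 4.3 gives 137 as the maximum N; the smaller values are assumptions to show the range.

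| N | Source | Change per man |
|---|---|---|
| 137 | SAP maximum | 100/137 = 0.73 points |
| 100 | Assumed | 100/100 = 1.00 points |
| 80 | Assumed | 100/80 = 1.25 points |
| 50 | Assumed | 100/50 = 2.00 points |

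If he were the only man with a year-2 SAE, the Newly SAE result at N = 137 would move from 0/137 (0.00%, exact 95% interval 0.00 to 2.66) to 1/137 (0.73%, 0.02 to 4.00).

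**The case against.** The strongest reply is that the case is rare. Grade and seriousness overlap heavily in Table 9-1, so an open Grade 1 or 2 event that leads to admission or disability would normally be regraded and would qualify as Newly. Exclusion criteria 4 and 7 and the laboratory limits at entry may also keep out some men with significant open events. This stands: it limits how often the fault occurs, and the true number may be zero. It does not make the column right when it does occur.

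A second reply is that the first part of the Newly definition already covers an event continuing into the extension. On that reading every open event would be Newly and the worsening clause would have no purpose, so onset is the workable reading. A third is that Protocol section 9.3 calls for a new report for an SAE at a different time interval. That sentence compares an SAE with a previous SAE; it does not address a continuing non-serious event that becomes serious. A site might still open a new record, but nothing instructs it to.

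Two stronger readings are tempting, and the documents support neither.

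- A reader might infer that the event is lost from the SAE table. That would require tabulating an outdated parent-study record. Protocol 6.1 (10) brings open events into the extension file, and SAP section 10.2 requires all SAEs to be listed. With the serious item updated, the event stays in Previous, Total and the listing. Protocol section 10.3 also promises a brief description of each SAE, which may reveal the timing in text.
- A reader might infer that the rule always understates year-2 SAEs. An event that was serious in year 1, is still open, and worsens modestly in year 2 without meeting any seriousness criterion qualifies as Newly. If it keeps its serious flag, it raises the Newly SAE count. The overall direction of error is therefore not established.

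**Conclusion.** The point holds as a misallocation between columns. Under SAP section 10.1 as written, a parent-study event that first becomes serious in the extension at an unchanged grade is counted under Previous and Total and not under Newly. This follows from the stated definition, so it is more than a missing detail.

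The effect is 0.73 percentage points of Newly SAE incidence per man at N = 137, and more if fewer men enter. The conclusion assumes that the event is kept as one record, that its serious item is updated in the extension file, and that its recorded grade does not rise. The documents give no count of open events at risk, so no total bias can be stated. The change is worth making because it corrects the definition behind the extension's SAE incidence at almost no cost.

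**What to change.** In SAP section 10.1:

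1. Define Newly as an event with onset after the first extension dose, or a pre-existing event that after that dose worsens in severity or first becomes serious.
2. Count as a Newly SAE only an event that met a seriousness criterion after that dose. This also stops a year-1 serious flag from carrying into the Newly SAE column when the event merely worsens.
3. State that linked Previous and Newly records count once in Total, as Protocol 6.1 (10) requires.

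In the case report form instructions, and preferably in Protocol 6.1 (10), ask the site to record the date on which the seriousness criterion was met, and show that date in Listing 16.2.7.3.

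The cost is a few sentences in the SAP, one date field or completion instruction, and linkage of a small number of records. Subject numbers carry over from the parent study, so the linkage is direct. No clinical procedure changes.
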